#### STUDY SPONSORSHIP

 1. Funding Sponsor:
 Specialized Research Center

 Department of Health and Human Services

 National Institutes of Health

 National Institute of Mental Health and the Office of Research on Women's

 Health, OD

#### 2. Primary Sponsor: same as above

#### INTRODUCTION AND PURPOSE

The overarching purpose of this study is to further our understanding of the individual and interactive effects of the hormone estrogen and the neurotransmitter serotonin on certain aspects of cognition and brain activation in menopausal women ages 48 to 60 years. Women will undergo cognitive testing and fMRI sessions both before and after 6 weeks of either estrogen or placebo administration. We will recruit women who are across the first 10 years and 11 months since their last menstrual period so that we can gather information regarding the potential impact of time since menopause on our outcomes of interest. We anticipate that findings from this study will help scientist and clinicians to refine their use of estrogen therapy in menopausal women. In addition, should the role of serotonin be of utmost importance for maintenance of healthy cognition, these data aid future drug development to preserve health cognition and/or to treat dementias in which serotonin is an important factor. This proposal is both novel and timely as results from this study are likely to provide information critical to the on-going discussion regarding the risks and benefits of ET use in menopausal women.

The aim of this study is to examine the interactive effects of estrogen and serotonin (5HT) on cognition, emotional processing, and brain activation. We will study the effects of acute tryptophan (TRP) depletion on cognition and mood in healthy menopausal women before and after estrogen replacement treatment (ERT). Using functional magnetic resonance imaging (fMRI), we will identify differences in brain activation during cognitive tasks with and without TRP depletion and before and after ERT in order to determine which brain regions and cognitive functions are affected by each manipulation.

#### OBJECTIVES

**Specific Aim 1:** To replicate and extend our previous behavioral findings of an interaction between ET and TRP-D on verbal memory in a group of early menopausal women randomized to receive ET (n=28). In a previous behavioral study of TRP-D and ET in healthy menopausal women (Amin et al., 2006b), we observed that TRP-D interfered with verbal memory to a lesser extent following ET than before. *In a new sample of women, we again hypothesize* (**H1.1**) *that paragraph recall performance and verbal paired-associates learning will decline as a result of TRP-D, but that ET will attenuate this decline.* In our previous study, we also found that length of hypogonadism (measured by months since last

menstrual period) was significantly associated with waning verbal memory performance. However, we did not have sufficient power with 18 women to detect whether the magnitude of ET effects differed based on length of time since menopause. *In this larger sample of 28 women, we hypothesize* (H1.2) *that women who have more recently experienced menopause will benefit more from ET than later menopausal women.* 

**Specific Aim 2:** To evaluate the extent to which effects of ET and TRP-D on verbal working memory are mediated through the dorsolateral prefrontal cortex. Previous neuroimaging studies have associated ET with improved working memory performance and increased dorsolateral prefrontal cortex (DLPFC) activation (Duff & Hampson 2000; Shaywitz et al., 1999). However, it is unclear whether TRP-D has an effect on working memory (Harrison et al., 2004; Riedel et al., 2003). It is hypothesized (**H2.1**) that ET will increase DLPFC activation during working memory more so than PT, but there will be no effect of TRP-D and no interaction between estrogen and serotonin effects in either the ET or PT groups. Very few fMRI studies have examined the impact of practice or rescanning on behavioral measures or the BOLD response during cognitive tasks. We seek to fill that void with the proposed study by including a placebo arm. Since submission of the A2 application, we have obtained test-retest data from our MR colleagues ([name], Ph.D.) demonstrating that with our new sample size of 28 women receiving ET and 14 women receiving placebo we can adequately test our hypothesis regarding ET and TRP-D effects on DLPC activation during the proposed working memory task.

**Specific Aim 3:** To determine the impact of adverse childhood events on brain activation during performance of the Emotion Identification (EmoID) and N-back Tasks pre and post ET and during sham and ATD. In healthy postmenopausal women, ET reverses the detrimental effects of ATD on verbal memory (Amin et al., 2006) and the impact of ATD on brain activation during cognitive an affective processing (Epperson, et al., 2007). ET will reverse the ATD related increase in amygdala activation to the EmoID Task while ET will reverse the ATD related decrease in dorsolateral prefrontal cortex (DLPFC) activation with the N-back Task in healthy, early postmenopausal women. This effect will be diminished in women with a score of  $\geq$  2 on the Adverse Childhood Event questionnaire (ACE).

**Note Regarding Exploratory Aims**: The following 2 aims have been relegated to an 'exploratory' status as this is now a 2-year grant and the sample size proposed herein may not be sufficient to adequately test this hypothesis. However, these data can be obtained at no additional costs as the main study expenses are related to recruitment and scans. Subjects will complete these tasks while in the scanner as described in the A2 application without increasing the subject burden above that of the previously reviewed application. These data will inform the development of additional RO1s aimed at examining the impact of ET on other aspects of verbal memory and affective processing in menopausal women.

**Exploratory Aim 1:** To evaluate the extent to which effects of ET and TRP-D on verbal memory are mediated through medial temporal lobe structures. TRP-D interferes with memory consolidation (McAllister-Williams et al., 2002; Park et al., 1994; Schmitt et al., 2000) and several studies have associated estrogen with improved verbal memory, possibly through effects on medial temporal lobe structures (Maki & Resnick 2000; Maki et al., 2001; Resnick et al., 1998; Shaywitz et al., 2003; Wolf et al., 1999). Again, there is little data examining the impact of practice or rescanning on behavioral measures or the BOLD response during a memory consolidation task. Our inclusion of a placebo group will fill the void and allow us to examine the effects that are specific to ET. We hypothesize (**HEA.1**) that hippocampal activation during sham and active depletion will differ during verbal encoding pre-ET, but not post-ET, when compared to the PT group. Within the two-year time frame of this study we will obtain sufficient data to more accurately determine the sample size necessary to adequately power

future investigations focusing on ET effects on the medial temporal lobe memory structures during verbal encoding.

**Exploratory Aim 2:** To evaluate the effects of ET and TRP-D on performance and brain activation during emotional processing. TRP-D has been associated with negative mood in certain vulnerable subjects and with bias toward negative stimuli (Klaassen et al., 2002). However, in our previous study (Amin et al., 2006a; see Preliminary Studies section, page 30), estrogen levels may be associated with brain activation indicative of bias toward positive stimuli. During an emotional go/no-go task, it is hypothesized (**HEA2.1**) that TRP-D will result in increased prefrontal cortex (PFC) activation to negative distracters, though this bias will be minimized in the ET group to a greater degree than in the PT group. Similarly, in response to an emotional face processing task, it is hypothesized (**HEA2.2**) that TRP-D will result in increased amygdala and orbitofrontal cortex activation to negative emotions, though this bias will be minimized following ET but not significantly following PT.

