# Figure 5: Multisubject data set showing (right) whole brain coverage moving from the bottom of the brain to the top in 16 slices.

The ASL approach has also been applied in a test/retest manner in order to get a sense of the reliability of this approach both between and

across subjects. The data show that the variance is regionally specific and that good within subject repeatability and excellent across subject repeatability are obtained (Figure 6). The data indicate that 16 subjects are required

to generate a p < 0.05 with a 40% increment in blood flow with activation, suggesting that we will have sufficient power to detect changes in blood flow as a result of ET or TRP-D.

Figure 6: Resting state CBF maps in 16 subjects scanned twice to generate inter- and intra-subject variance maps for CBF. The colorbar represents the number of subjects required to obtain a p<0.05 level of significance corrected for multiple comparisons in the awake state.

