# fMRI Studies of Menopausal Women Undergoing TRP-D and ET

To date we have pilot data collected on 9 subjects; this data is from the PIs study at the Yale University School of Medicine. This data was used for our R01 grant submission. The figures below include data from 6 of the 9 subjects. One subject withdrew before her first test day could be scheduled and another was excluded when we decided to limit our recruitment to women 10 years within LMP. A third subject discontinued estrogen during travel between Test Day 3 and Test Day 4. Thus, we have full data from 6 subjects who completed all 4 test days. It is very important to reiterate that this sample size is too small to conduct meaningful statistical analyses. These data are presented solely to demonstrate 1) our ability to conduct the proposed study, 2) that the experiments are appropriately designed to investigate BOLD signal changes within the regions of interest, and 3) to show similar changes in activation across subjects across test days, supporting that we will find group effects.

To demonstrate these effects, we have conducted a preliminary group analysis to identify similarities in activation in regions of interest (p<0.05 uncorrected). We include the data below as they demonstrate differences **between test days** and the **individual effects of TRP-D** on brain activation during the 2-back verbal working memory task. (Rt ACC shown in figure)

Figure 5: Prior to ET, Active TRP-D resulted in decrease in ACC activation in the 2-back verbal working memory task.

In order to examine the **individual effects of ET** on verbal working memory, we compared brain activation on sham depletion test days pre-ET and post-ET. As reported in our previous application, we continue to see ET-enhancement in DLPFC activation during the 2-back test.

Figure 6: ET enhanced activation in the DLPFC on the 2-back test.

Figure 7: Supporting our hypothesis, there was a decrease in right amygdala activation during the faces task (angry relative to neutral) on post-ET sham test days compared to pre-ET sham test days.

p < 0.05, FDR-corrected, masked for amygdala

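### H2.1 predicts no depletion effect and no estrogen-by-depletion interaction on DLPFC activation, Aim 3 predicts or presupposes both, and the plan neither ranks the two nor says what would support the null

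*Combined protocol and SAP*

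**What the plan says.** In the Objectives, Specific Aim 2 concerns verbal working memory and the DLPFC. H2.1 expects ET to raise DLPFC activation more than placebo treatment (PT) does. For tryptophan depletion it adds that "there will be no effect of TRP-D and no interaction between estrogen and serotonin effects in either the ET or PT groups". The same paragraph explains the placebo arm by the lack of data on practice and rescanning ("We seek to fill that void with the proposed study by including a placebo arm") and, citing colleagues' test-retest data, states that "with our new sample size of 28 women receiving ET and 14 women receiving placebo we can adequately test our hypothesis" about ET and depletion effects.

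Specific Aim 3, on childhood adversity, states that "ET will reverse the ATD related decrease in dorsolateral prefrontal cortex (DLPFC) activation with the N-back Task in healthy, early postmenopausal women". It continues "This effect will be diminished in women with a score of" 2 or more on the ACE questionnaire. The note after Aim 3 says "The following 2 aims have been relegated to an 'exploratory' status". That refers to the two exploratory aims listed after it, so Aims 2 and 3 both remain Specific Aims.

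The Statistical Analysis section plans thresholded activation maps (P = .05 with small-volume correction for a priori regions), a repeated-measures ANOVA for the depletion-by-estrogen interaction, and simple-effects analyses.

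**The concern.** A depletion-related decrease is a depletion effect, and its reversal by ET is an ET-by-depletion interaction. H2.1 says neither will occur in that region. If depletion lowers DLPFC activation and ET reverses it, Aim 3 is met. If both terms are non-significant, the depletion part of H2.1 appears to be met. With no ranking, a reader cannot tell which prediction was confirmatory, and opposite results could each be presented as expected.

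The second part concerns H2.1's null. Every planned test looks for a difference, and the plan has no margin, confidence-interval rule or other criterion for concluding that an effect is absent. A non-significant term may reflect no effect or too little precision.

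**Working it through.** **The two aims side by side**

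- *Region and manipulation.* Both sentences concern the DLPFC. TRP-D and ATD are both acute tryptophan depletion.
- *Task.* The pilot section describes depletion effects "on brain activation during the 2-back verbal working memory task", so the verbal working-memory task is the 2-back. The analysis section lists verbal and figural 2-back. Aim 3 says only N-back, and no aim is assigned a version. Overlap is very likely but not stated.
- *Other text.* The Background calls the effect of depletion on working memory unclear. The pilot (6 women, uncorrected) shows a depletion decrease in the anterior cingulate, not the DLPFC. Neither settles which prediction governs.
- *Adequacy.* The allocation is 28/14 = 2:1, 42 in total. The adequacy statement cannot be reproduced, because no SD, effect size or power accompanies it. The analysis section's power statement concerns signal detection with 10 subjects. Another, "suggesting that we will have sufficient power to detect changes in blood flow as a result of ET or TRP-D", concerns perfusion.

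**Illustration of precision**

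Assumptions: the unit is the SD of one woman's active-minus-sham difference; single two-sided 5% tests; normal data; no dropout and no small-volume correction (either would lower precision or power).

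Pre-treatment depletion effect, half-width t(.975, n−1)/√n:
- n = 42: 2.020/6.481 = 0.31.

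Interaction, meaning the pre-to-post change in that difference. Its SD is √(2(1−ρ)), where ρ correlates a woman's pre and post differences. Equal variances and correlations across the four sessions give ρ = 0 and a ratio of 1.41. The range taken is ρ = 0.5 (ratio 1.00) to ρ = −0.2 (ratio 1.55).
- Within ET, n = 28: 2.052 × 1.414/5.292 = 0.55.
- ET versus PT: 2.021 × √(1/28 + 1/14) × 1.414 = 2.021 × 0.327 × 1.414 = 0.94; range 0.66 to 1.02.

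Now suppose Aim 3 is true: depletion lowers activation by d, ET fully reverses it, and PT changes nothing. Noncentral-t probabilities of a non-significant result, with the joint row simulated:

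| Contrast | d = 0.5 | d = 0.8 |
|---|---|---|
| Pre-treatment depletion, n = 42 | 11% | 0.1% |
| Interaction within ET, n = 28, ρ = 0 | 56% | 18% |
| Interaction ET versus PT, ρ = 0 | 82% | 61% |
| Same, over the ρ range | 68–84% | 34–66% |
| Pre-treatment depletion and ET versus PT both non-significant, over the ρ range | 8–10% | under 0.1% |

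For example, ET versus PT at d = 0.5 has noncentrality 0.5/(1.414 × 0.327) = 1.08 on 40 df and power 18%.

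**The case against.** The best defence is that the Aim 3 sentence carries no hypothesis label, follows citations of earlier results, and sits under an aim about childhood adversity. H2.1 is the labelled hypothesis and would govern. That reading is possible, but the text does not state it, and it leaves a conflict: Aim 3 next predicts that the effect is weaker at higher ACE scores, and under H2.1 there is no DLPFC effect to weaken. Weakening it in some women also requires it in others.

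Three stronger readings are tempting and are not supported:

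- *A true Aim 3 effect would usually pass as agreement with H2.1.* The 82% invites this, but H2.1's null needs both terms to be absent. In the illustration both are non-significant in only 8 to 10% of trials at 0.5 SD. Averaging depletion over pre and post sessions raises this to at most about 23%. The 82% also belongs to a between-arm contrast that neither hypothesis sentence names. H2.1 is worded within arm, where the ET figure is 56%.
- *28/14 is inadequate.* The test-retest data behind the adequacy statement are not in the documents, so inadequacy is not shown.
- *The plan will report non-significance as no effect.* It does not say so. It only lacks a rule against it.

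**Conclusion.** The inconsistency stands and needs no calculation. Two Specific Aims make incompatible statements about depletion, and about its interaction with estrogen, for DLPFC activation on what is very likely the same task, and nothing in the plan chooses between them. That difference tests alone cannot support H2.1's null also stands.

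The sizes depend on the assumed SD structure and effects. They show that the interaction, with a half-width about three times that of pre-treatment depletion (0.94 against 0.31), is the imprecise part of the null. An Aim 3 effect of 0.5 SD or more would usually contradict H2.1 through the depletion effect. This should be fixed before analysis.

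**What to change.** - State which N-back version each aim concerns. Name one confirmatory prediction for the depletion effect and one for the ET-by-depletion interaction on DLPFC activation.
- If the Aim 3 sentence is only a premise for the ACE question, say so, and say what the ACE analysis means if that effect is absent.
- Estimate pre-treatment depletion in all 42 women. Make the randomised ET-versus-PT difference in the pre-to-post change of the depletion effect the main interaction contrast. Keep within-arm contrasts descriptive, because practice and rescanning are the stated reason for the placebo arm.
- Test two-sided and report 95% CIs. Report non-significance as not shown unless the 90% CI lies inside a margin fixed beforehand for that contrast. One margin cannot serve both: with a true effect of zero and ρ = 0, 80% equivalence power needs 0.46 for pre-treatment depletion and 1.38 for ET versus PT.
- Replace or qualify the adequacy statement with expected half-widths for these contrasts, if the test-retest data support them. The protocol does not say that those data include depletion sessions. If they do not, state the SD as an assumption with a range.

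The cost is wording in Aims 2 and 3 and in the analysis section, plus the half-width calculation. The sponsor gives up claiming support for the null from non-significance, and the interaction null will probably be reported as not shown.

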#### BACKGROUND

The menopause may be marked by changes in cognition and mood in addition to wellcharacterized vasomotor and urogenital symptoms (Devi et al., 2005; McVeigh 2005; Peeyananjarassri et al., 2006; Schnatz et al., 2006). While the administration of estradiol can relieve depressive symptoms (Schmidt et al., 2000; Soares et al., 2001) and may improve cognitive symptoms, particularly when used early in the menopausal transition (Sherwin 2003), the mechanisms by which estrogen modulates cognition and mood are still unclear. There is evidence of estrogen's interaction with the neurotransmitter serotonin (review in Amin et al., 2005), which is hypothesized to be involved in depression and various cognitive processes. Studies in animals have suggested decreased serotonin transporter (Kakiuchi et al., 2001) and receptor (Nyakas et al., 1997) binding with aging, and that treatment with serotonin precursors reduces age-related cognitive decline (Richter-Levin and Segal, 1996). Studies in humans also show changes in the serotonin system with aging (McEntee and Crook 1991; Palmer and DeKosky, 1993) and associations between cognitive decline in Alzheimer's disease, decreased serotonin levels, and changes in density of certain serotonin receptors (Lai et al 2005; Lai et al 2002). Furthermore, it is possible that there are sex differences in the effects of serotonin on cognition in aging, with women more likely to benefit from increased serotonergic transmission than men (Munro et al., 2004). Research in animals indicates that estrogen enhances serotonin transmission (review in Bethea et al., 2002) and observational evidence in humans has suggested that estrogen treatment may decrease the risk for Alzheimer's disease if initiated early (Henderson et al., 2005), suggesting a possible link between estrogen and age-related changes in the serotonin system. However, there is little information about estrogen-serotonin interactions in humans, largely because there are few methods that allow manipulation of both estrogen and serotonin.

The results of the proposed study are expected to provide insights regarding the clinical use of estrogen in healthy menopausal women. By examining the effects of estrogen treatment in women within 10 years of their last menstrual period, we aim to evaluate whether estrogen administration can improve certain aspects of cognition in women along the peri- and early menopause stages of life. *While the study proposed in this present application will not provide definitive information regarding 'when' and 'how long' women should use ET for cognitive benefits, it will provide data to guide future investigations. In addition, our findings are expected to further our understanding of the individual and interactive effects of estrogen and serotonin on specific aspects of cognition and brain regions thought to underlie those processes.*  Previous studies have found interactions between treatment with estrogen and with selective serotonin reuptake inhibitors (SSRIs). For example, administration of fluoxetine was found to suppress circulating estradiol levels and estradiol treatment-related enhancement of spatial memory in ovariectomized rats (Taylor et al., 2004). Whether the cognitive changes associated with this drug-hormone interaction were due to changes in estradiol level and/or secondary to primary neuronal effects could not be determined. As these rodents were acutely hypogonadal, it is not known whether the same interaction between SSRI and estrogen would occur with the gradual decline in estrogen characterized by a natural menopause. In the human laboratory, women with hot flashes and depressive symptoms demonstrated a better symptom reduction with low-dose conjugated equine estrogen (CEE) treatment plus fluvoxamine than with CEE treatment alone (Nagata et al., 2005). Whether fluvoxamine alone compared to CEE alone was more effective in the treatment of hot flashes and depressive symptoms was not addressed by the investigators. However, these findings suggest that for women experiencing vasomotor and mood symptoms in the menopause, a regimen that combines estrogen with a SSRI may be preferable.

Studies of ET in menopausal women indicate increased serotonin activity, (Halbreich et al 1995; Lippert et al 1996; Sherwin and Suranyi-Cadotte 1990; van Amelsvoort et al., 2001), improved mood (Schmidt et al., 2000; Soares et al., 2001), and, despite some inconsistencies across measures and hormone regimens, improved performance in cognitive domains such as verbal learning and memory (Hogervorst et al., 2000; LeBlanc et al., 2001; Rice and Morse 2003). In addition, estrogen-induced changes in the serotonin system have been found coincident with mood or cognitive changes (Kugaya et al., 2003; Sherwin and Suranyi-Cadotte 1990). Thus, the literature suggests a correlation between estrogen and serotonin activity and a change in mood or cognition in humans, but causation is unclear. It is possible that the regulatory activity of estrogen on the 5-HT system decreases if estrogen levels are low, contributing to the vulnerability of menopausal women to changes in mood and cognitive deficits. By combining ET, tryptophan depletion procedures, and functional magnetic resonance imaging (fMRI), it is possible to safely manipulate both estrogen and serotonin in humans, and non-invasively evaluate their individual and joint effects in the brain.

The acute tryptophan depletion (TRP-D) paradigm, a manipulation which results in rapid reduction of brain TRP and 5-HT levels, has been successfully used in human studies as a probe of central 5-HT function. Sex differences in response to acute TRP-D have been identified, suggesting hormonal influences on the serotonin system. For example, a PET study demonstrated that the rate of serotonin synthesis decreased significantly more in women than in men undergoing TRP-D (Nishizawa et al., 1997). In addition, a study of twenty healthy women found that TRP-D resulted in significant worsening of mood, though data from healthy men had shown no significant change (Ellenbogen et al., 1996). Given the likelihood that sex hormones modulate response to the TRP-D procedure, the combination of ET and TRP-D is expected to reveal interactions between estrogen and serotonin.

